13.2 Exclusion criteria

Patients must not enter Combination Module 1 of the study if any of the exclusion criteria apply. Please also refer to Section 5.2 for the exclusion criteria applicable to all modules in the study. If the criteria in the modules is different from that in the Core Module criteria,

the module-specific criteria should be followed. Exclusion criteria applicable to Combination Module 1 only are described in this section.

Part A and B

- 1 Any contraindication to the PLD or any excipients as per local prescribing information eg, hypersensitivity.
- 2 Patients who have had drainage of their ascites during the preceding 4 weeks prior to enrolment of the study (patients with indwelling peritoneal catheters are permitted).
- 3 Patients who have had a previous CTCAE Grade \geq 4 haematological toxicity with PLD.

Part B only

- 1 Patients with platinum refractory disease (defined as disease progression whilst receiving first-line platinum-containing therapy or within 1 month of completion).
- 2 Prior anthracycline therapy, including prior treatment with PLD in any setting.
- 3 History of clinical symptoms requiring hospital admission for acute bowel obstruction within 3 months of study enrolment.
- 4 History of abdominal fistula, GI perforation, intra-abdominal abscess, rectosigmoid or bowel involvement eg, bowel invasion on CT.
- 5 Prior (or anticipated need for) radiotherapy to pelvis or abdomen, major surgery anticipated during study treatment or within 4 weeks before starting study treatment.

13.3 Lifestyle restrictions

Restrictions for PLD should follow the institutional guidelines.

Please refer to Appendix G for contraception restrictions.

14 STUDY TREATMENTS

Study treatment in Combination Module 1 refers to AZD7648 and PLD (Table 14).

14.1 Treatments administered

14.1.1 Investigational products

Table 14Study treatments

Study treatment name:	AZD7648	Pegylated liposomal doxorubicin
Dosage formulation:	Provided as mg, mg, mg, mg, mg, and mg white film-coated oral tablets. The mg and mg tablets are round. The mg and mg tablets are caplet shaped. Note: In accordance with Quality IMPD, other intermediate strengths may be added at a later date.	2 mg/mL suspension/dispersion for IV use (eg, Caelyx, Doxil or equivalent).
Route of administration:	Oral tablets	IV infusion
Starting dose instructions:	The starting dose of AZD7648 is dependent on emerging data from the Core Module. AZD7648 will be administered CCI of PLD.	The starting dose of PLD is 40 mg/m ² , administered by IV infusion once every 4 weeks, for a maximum of 6 cycles.
Packaging and labelling:	Study treatment will be provided in high-density polyethylene bottles with child-resistant polypropylene screw caps. Each bottle will be labelled in accordance with Good Manufacturing Practice Annex 13 and per country regulatory requirement. Label text will be translated into local language. The site must complete the Patient Diary with the details of the dosing instructions at the time of dispensing.	The site must complete the Patient Diary with the details of the dosing instructions at the time of dispensing.
Provider:	AstraZeneca	Sourced by site

14.1.2 Dose escalation scheme

For Combination Module 1, the dose escalation schedule is presented in Figure 9. When there is more than one patient enrolled to a dose cohort, sentinel dosing will be applied with a single patient exposed for a minimum of 48 hours after Cycle 1, Day 1 before further patients are enrolled at that dose level. In the absence of any significant toxicities in the first patient, the patients for the remainder of the cohort may be enrolled, concurrently or sequentially, based upon the decision of the SRC.

For each cohort in dose escalation a SRC will review the safety of the first and each subsequent cohort.

Figure 9AZD7648 combinations study flow chart

RP2D=recommended Phase II dose

The starting dose of PLD is 40 mg/m², administered by IV infusion once every 4 weeks, for a maximum of 6 cycles (Table 15). Patients who are deriving clinical benefit may continue AZD7648 beyond 6 cycles as monotherapy in the continuation phase; using a dose and schedule declared tolerated in the Core Module.

During Part A (dose escalation), a single dose of AZD7648 will be administered to enable collection of blood samples for PK analyses, followed by a drug washout of CCI (Figure 10). The dose of PLD may also be escalated to 50 mg/m² (or de-escalated to 30 mg/m²) every 4 weeks with agreement of the SRC. Intermittent schedules for AZD7648 will also be explored.
Cohort	PLD dose (mg/m ²)	AZD7648 dose CC (mg)	No. days of AZD7648 in each cycle
-1	30	CCI	E
Starting Cohort 1	40	CCI	T
2	40	CCI	•
3	40	CCI	e.
4	40	CCI	CC .
Cohort n	40	Escalate to monotherapy MTD or MFD in no more than 50% increments	
Maximum dose level	50	CCI	CCI

Table 15 Illustrative AZD7648 dose escalation schedule

CCI=**CCI**; MFD=maximum feasible dose; MTD=maximum tolerated dose; PLD=pegylated liposomal doxorubicin.

Actual doses and schedules may vary using Bayesian adaptive design modelling based on emerging safety and tolerability data, and subject to Safety Review Committee (SRC) agreement. The dose of PLD may also be escalated to 50 mg/m^2 (or de-escalated to 30 mg/m^2) administered once every 4 weeks.

For Combination Module 1, informative prior estimates of dose-toxicity relationship from relevant internal and external studies will be combined with prior estimates of AZD7648 dose-toxicity relationship emerging from the Core Module (monotherapy) of the study. The model incorporates terms for each monotherapy and for the combination (interaction term). A non-informative prior will be used for the interaction term.

A minimum of 3 and a maximum of 6 patients per cohort will be enrolled in Part A cohorts. For SRC meetings prior to dose escalation where 3 patients have been enrolled, at least 2 patients will need to be evaluable for DLT. However, if patients are receiving treatment within the DLT assessment period, the dose escalation review meeting should be deferred so that the SRC accounts for all patient data. Additional CRF data may be included in the SRC review including vital signs, clinical chemistry / haematology, ECG results, PK and PD data, ad hoc safety reports, AEs from previous cohorts and optional expansions and any other emerging data.

Dose escalation and de-escalation will follow the Bayesian adaptive design described in Section 6.1.2.

14.2 Treatment compliance

PLD will be administered on site and will be recorded in the appropriate section of the CRF.

14.3 Concomitant therapy

14.3.1 Effect of pegylated liposomal doxorubicin on other drugs

No formal medicinal product interaction studies have been performed with PLD, although Phase II combination trials with conventional chemotherapy agents have been conducted in patients with gynaecological malignancies. Exercise caution in the concomitant use of medicinal products known to interact with standard doxorubicin hydrochloride. PLD, like other doxorubicin hydrochloride preparations, may potentiate the toxicity of other anti-cancer therapies. During clinical trials in patients with solid tumours (including breast and ovarian cancer) who have received concomitant cyclophosphamide or taxanes, no new additive toxicities were noted. Caution must be exercised when giving any other cytotoxic agents, especially myelotoxic agents, at the same time.

14.4 Dose modification

Refer to Section 6.6 for management of treatment related toxicity applicable to all study modules.

If the toxicity does not resolve to the patient's baseline or to CTCAE Grade ≤ 2 within 28 days of onset, treatment with AZD7648 and PLD must be discontinued. However, if toxicity is clearly attributed to PLD alone, the patient is permitted to continue receiving AZD7648 as monotherapy following discussion between the Investigator and the AZ Study Physician. If PLD is discontinued due to reasons other than toxicity, AZD7648 monotherapy may continue following discussion between the Investigator and the AZ Study Physician.

15 STUDY ASSESSMENTS AND PROCEDURES

Study procedures and their timing are summarised in the SoA (Table 13).

15.1 Management of study treatment-related toxicities

At this time, there are limited safety data regarding the combination of AZD7648 and PLD. Given the differing mechanisms of action of AZD7648 and PLD, the potential for potentiation of toxicities is thought to be limited. Some toxicities, for example pneumonitis and asthenia/fatigue may, on theoretical grounds, be potentiated in the combination arm and particular attention should be paid to these.

In the event of toxicity in this combination module of the study which cannot be managed by supportive measures alone, stopping one or both study treatments should be an Investigator decision based on the available information and, if necessary, following discussion with the Sponsor.

The following general guidance should be followed for management of toxicities:

- Treat each of the toxicities with maximum supportive care (including withholding the agent suspected of causing the toxicity if required).
- If the symptoms promptly resolve with supportive care, consideration should be given to continuing the same dose of the assigned study treatment along with appropriate continuing supportive care. If medically appropriate, dose modifications are permitted for AZD7648. In addition, guidelines on AZD7648 dose modifications are provided in Section 6.6 and 14.4. In the event of toxicity that cannot be managed by following the toxicity management guidelines for AZD7648 and PLD, consider stopping treatment.

All dose modifications should be documented with clear reasoning and documentation of the approach taken.

Management of PLD related toxicities will be performed in accordance with local practice.

15.2 Echocardiogram

An echocardiogram or MUGA scan will be conducted on all patients at screening for Parts A and B, and at the timepoints in the SoA (Table 13). The screening echocardiogram or MUGA scan will not be required if a previous echocardiogram or MUGA scan was performed 6 months prior to screening, unless there has been a change in the patient's cardiac status.

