Section 6.1.2.1 the text related to administration of study drug and the fasted state in the food effect expansion cohort has been revised to be consistent with text in Appendix I. The time interval between Cycle 0, Day 1 and Cycle 1, Day 1 in both Section 6.1.2.1 and Appendix I has been updated to 72 hours to allow for adequate washout. In this section the following sentence has also been deleted: Patients with insulin-dependent diabetes must be excluded from the food effect cohort, as this has been added as a new Exclusion Criterion.

Section 6.1.3 the grade for haematological toxicities for neutropenia and thrombocytopenia have been updated from grade 3 to grade \geq 3 and therefore the lower limits have been removed. Units are also presented as mm³ and 10⁹/L. These changes are also applied to Section 22.1.

Section 8.4.2.1 clarification added that patients who become pregnant should be discontinued from study treatment but not from the study.

 Table 10, Table 11, Table 12, and Table 17 have been updated to clarify post dose sampling timings for PK/CCI

Section 8.6.3 the tumour biopsy collection times have been updated in line with the footnote on the SoA.

Section 9.2 has been updated to correct the cohort size from n = 3 to 6 to n = 1 to 6.

Section 9.4.1 has been modified to clarify that the starting point for the efficacy analyses for progression-free survival and overall survival should be the first dose at Cycle 1.

Table 13 has been revised to remove the TNBC arm and remove the subset of patients with

 HRR*m*-enriched ovarian cancer from the interim analysis for Combination Module 1.

Table 14 (SoA for Combination Module 1) has been updated as follows:

- **Parts A and B** have been updated to correct the cross-reference for echocardiograms (section 8.2 did not include details). **Section 15.2** has been added to describe echocardiograms.
- **Parts A and B** have been updated to include a tumour assessment from Cycle 3 and onwards Visits. The tumour assessment at the IP Disc Visit has been removed from Part A to be consistent with the other SoAs.
- **Part B** has been updated to add sample collections for ^{CCI} and CCI at the Cycle 1 Day 8 Visit, and to update the footnote for the CCI sample at the Cycle 1 Day 15 Visit.

• **Parts A and B** have been updated to revise the AZD7648 dosing in line with updates made in Table 16. The footnotes are also updated to clarify dosing.

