5 STUDY POPULATION

Prospective approval of protocol deviations to recruitment and enrolment criteria, also known as protocol waivers or exemptions, are not permitted.

Each patient should meet all of the inclusion criteria and none of the exclusion criteria for the core and Combination Module 1 (if applicable). **Under no circumstances can there be exceptions to this rule.** If there are differences in cut-off values, the specific module takes precedence. For example, if the haematological parameters are stricter in the combination module rather than the Core Module, the Investigator should adhere to the combination module criteria. Patients who do not meet the entry requirements are screen failures, refer to Section 5.4.

For procedures for withdrawal of incorrectly enrolled patients see Section 7.3.

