5.2 Exclusion criteria

The exclusion criteria that are applicable to all parts/cohorts of the study are described in this section. Please also refer to Section 13.2 for additional specific criteria applicable to Combination Module 1.

Medical Conditions

- 1 Any unresolved toxicities from prior therapy CTCAE Grade ≥ 2 (with the exception of alopecia).
- 2 Spinal cord compression or brain metastases unless definitively treated (minimum of 3 weeks between completion of radiotherapy and first dose of study treatment and recovery from acute toxicity Grade ≥ 2), asymptomatic, stable (no clinical evidence of progression since completion of central nervous system-directed therapy) and not requiring steroids for at least 4 weeks. Disease outside the central nervous system must be present.
- 3 As judged by the Investigator, any evidence of severe or uncontrolled medical conditions including but not limited to:
 - Uncontrolled diabetes mellitus, uncontrolled seizures, active infection requiring systemic antibiotics, antifungal or antiviral drugs, severe chronic obstructive pulmonary disease, severe Parkinson's disease, active inflammatory bowel disease, psychiatric condition, active bleeding diatheses, renal transplant, or active infection including any patient with active hepatitis B, hepatitis C or human immunodeficiency virus.
- 4 Any other malignancy which has been active or treated within the past 3 years, with the exception of in situ cancer of the cervix, non-melanoma skin cancer, ductal carcinoma in situ, Stage 1 Grade 1 endometrial carcinoma, or other solid tumours including lymphomas (without bone marrow involvement) curatively treated with no evidence of disease for ≥ 5 years.
- 5 Refractory nausea and vomiting or unable to swallow and retain oral medication, chronic GI diseases or previous bowel resection with clinically significant sequelae that would preclude adequate absorption of AZD7648, GI symptoms CTCAE Grade > 1, history of

GI ulceration and gastrointestinal haemorrhage within 6 months of first study drug administration.

Prior/Concomitant Therapy

- 6 Receiving or having received anti-cancer treatment within the following periods prior to the first dose of investigational product:
 - (a) Cytotoxic treatment: 3 weeks
 - (b) Non-cytotoxic drugs, including small molecule investigational products: 3 weeks or 5 half-lives (whichever is longest)
 - (c) Biological products including investigational immuno-oncology agents: 4 weeks

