8 STUDY ASSESSMENTS AND PROCEDURES

Study procedures and their timing are summarised in the SoA.

The Investigator will ensure that data are recorded on the CRF. The Web Based Data Capture system will be used for data collection and query handling.

The Investigator ensures the accuracy, completeness and timeliness of the data recorded and of the provision of answers to data queries according to the Clinical Study Agreement. The Investigator will sign the completed CRF. A copy of the completed CRF will be archived at the study site.

Immediate safety concerns should be discussed with the Sponsor immediately upon occurrence or awareness to determine if the patient should continue or discontinue study treatment.

Adherence to the study design requirements, including those specified in the SoA, is essential and required for study conduct.

All screening evaluations must be completed and reviewed to confirm that potential patients meet all eligibility criteria. The Investigator will maintain a screening log to record details of all patients screened and to confirm eligibility or record reasons for screening failure, as applicable.

Procedures conducted as part of the patient's routine clinical management (eg, blood count) and obtained before signing of the ICF may be utilised for screening or baseline purposes provided the procedures met the protocol-specified criteria and were performed within the time frame defined in the SoA.

The number of samples taken, as well as the volume required for each analysis, may be changed during the study as emerging data become available. However, the estimated total volume of blood that will be drawn from each patient in this study during screening and the first cycle of treatment will not exceed approximately 350 mL (over a 1 month period). Any additional requirements are specified within the relevant section of Combination Module 1. Safety laboratory assessments will be performed locally at each centre's laboratory by means of their established methods. Therefore, the number of samples/blood volumes is patient to site-specific change.

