^a 1 cycle = 28 days. Cycles repeat on a continuous basis with no interval between cycles.

^b Weekly visit may be omitted if Visit Y is within 2 days of weekly visit.

• Visit Y is only utilised if the dosing schedule is intermittent. Visit Y represents the last AZD7648 dosing day in the first block of AZD7648 treatment in a cycle eg, CCI

^d There are no visit windows in Cycle 0 and Cycle 1.

- e With the patient's consent, as part of the medical history, any available information on known tumour gene mutations will be collected.
- f Targeted physical examinations only required if clinically indicated (indication should be stated).
- ^g Vital signs then ECG measurements will be collected prior to PK blood draws at all PK sample timepoints. Timepoints may be modified based on the initial data obtained.
- ^h Serious adverse events (SAEs) only to be collected between AZD7648 discontinuation and disease progression.
- ⁱ Women of child-bearing potential must have a negative urine or serum pregnancy test at screening, a confirmatory test before treatment on Day 1 (Cycle 0 or Cycle 1), at regular intervals during treatment and at AZD7648 discontinuation. If results are positive, the patient is ineligible/must be discontinued from the study treatment and not discontinued from the study. The patient will continue to be followed up according to the study protocol.
- ^j TSH to be measured at baseline and every 3 cycles. CRP to be collected at baseline, then on Day 1 from Cycle 1. Urinalysis at Cycle 0, Cycle 0 + 1 and Day 1 of each cycle. Tumour markers (if relevant) to be measured at baseline and on Day 1 of every cycle from Cycle 1 (only if elevated at baseline).
- k LVEF assessment (ECHO or MUltiGated Angiography [MUGA]) and review must occur at screening and prior to dosing at Cycle 4 Day 1 and Cycle 7 Day 1 (-7 day window).
- ¹ Provision of archival tumour samples are mandatory for all patients. The samples may be submitted retrospectively.
- ^m Fresh biopsy samples are encouraged in Part A (particularly in patients with accessible tumours) and are mandatory for patients enrolled into Part A optional PD expansion cohorts (or a PD subgroup of an optional efficacy expansion cohort). Serial biopsies will be collected during screening, on treatment (any time in Cycle 1 between Days 3 and Visit Y 2 to 8 hours [h] post AZD7648 dosing), and on progression.

		-	-	 	
n	CCI				
0	I CCI				

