12 STUDY DESIGN

12.1 Overall design

Combination Module 1 will evaluate the safety, tolerability, PK, PD, and preliminary efficacy (anti-tumour activity) of AZD7648 (given orally) in combination with PLD (given IV) as below:

Part A: Dose escalation of AZD7648 in combination with PLD in approximately 30 evaluable patients with advanced solid tumours in whom PLD is an appropriate therapy. Prior information for PLD toxicity will be based on the locally approved label, whilst prior information for AZD7648 toxicity will be based on emerging data from the monotherapy arm (Core Module).

The starting dose of PLD will be 40 mg/m² administered IV once every 4 weeks for up to 6 cycles. Patients who respond or have stable disease following 6 cycles of PLD, are permitted to continue AZD7648 at the monotherapy RP2D (or lower dose) from the Core Module during the 'continuation phase'. Although AZD7648 is administered continuously as monotherapy, it is anticipated that an intermittent schedule will be required in combination. Two intermittent schedules that may be explored, including but not limited to, are: i) an intermittent within cycle schedule starting from CCL dosing eg, days off, and/or ii) an CCL days off. The duration and/or frequency of dosing for

both schedules may be altered based on emerging data and multiple schedules may be run concurrently if agreed by the SRC.

The PLD dose is consistent with local clinical practice (common usage of 40 mg/m²).

Part B: A safety and PoC Phase 2a expansion is planned to assess the combination in approximately 37 evaluable patients with advanced ovarian cancer who have relapsed within 12 months of completing a platinum-containing therapy. This includes patients who have platinum-resistant disease who have not received more than one cytotoxic regimen for platinum-resistant disease and patients with partial platinum sensitivity.

Sites must send formalin-fixed paraffin embedded (FFPE) tissue for retrospective central laboratory confirmation of advanced ovarian cancer.

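### Combination Module 1 Part A: the Section 15.2 waiver of the screening ECHO/MUGA does not lapse after intervening anthracycline, so the LVEF that qualifies a patient for PLD can predate that exposure

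*Protocol*

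**What the plan says.** **The waiver.** Protocol 15.2 schedules an echocardiogram or MUGA scan at screening for Parts A and B. It then says the scan "will not be required if a previous echocardiogram or MUGA scan was performed 6 months prior to screening", and the only thing that cancels this is a change in the patient's cardiac status. The ECHO row of Table 13 (Section 10.1) points to 15.2, and the Version 4.0 history records that the section "has been added to describe echocardiograms".

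**The schedule.** Table 13 footnote k says LVEF assessment and "review must occur at screening and prior to dosing at Cycle 4 Day 1 and Cycle 7 Day 1", with no exception. Section 8 accepts procedures done before consent only if they "were performed within the time frame defined in the SoA", and screening there runs from Day -28 to Day -1.

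**Entry criteria that bear on it.**
- Section 13.1, inclusion 3 (Parts A and B) requires LVEF above the institutional lower limit of normal by ECHO or MUGA. It gives no date limit.
- Section 5 makes module criteria override Core ones: "If there are differences in cut-off values, the specific module takes precedence".
- Section 13.2 excludes prior anthracycline, including PLD, under Part B only. For both parts it excludes previous Grade 4 or worse haematological toxicity with PLD.
- Section 5.2, exclusion 6(a) sets the washout: "Cytotoxic treatment: 3 weeks".
- Section 12.1 describes Part A as "patients with advanced solid tumours in whom PLD is an appropriate therapy".

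**The analysis.** ECHO is a primary safety variable for this module (Protocol Section 3; SAP Table 1). SAP 3.2.1.12 summarises LVEF change from baseline by visit and in ten change categories.

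**The concern.** An LVEF check before PLD is there to show that the heart can take an anthracycline. The protocol recognises the class risk: Sections 11.1 and 11.2.1.1 describe PLD as less cardiotoxic than the unencapsulated drug, not free of cardiotoxicity. If a patient received anthracycline after the accepted scan, that scan cannot show what the exposure did.

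The waiver turns on a change in cardiac status. Receiving a cardiotoxic drug is not in itself such a change, and an asymptomatic fall in LVEF is normally found by the very scan being waived. A site could follow 15.2 to the letter and admit a patient whose current LVEF is below the required limit. The next scheduled measurement is at Cycle 4 Day 1, after three cycles of PLD.

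**Working it through.** The plan gives no figure to reproduce. The check has two parts: whether the route is open on the text, and how old the scan can be.

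**1. Is the route open in Part A?**
- Prior anthracycline is excluded for Part B only. The exclusion common to both parts, for severe haematological toxicity with PLD, would be pointless unless some PLD-treated patients could enter Part A.
- Inclusion 3 demands a normal LVEF but does not say when it was measured.
- Core exclusion 10 covers infarction, NYHA Class II to IV heart failure, unstable angina and unstable arrhythmia within 6 months of entry. Core exclusion 11(a) covers a known reduced LVEF. Exclusion 1 ("Any unresolved toxicities from prior therapy CTCAE Grade" 2 or worse) covers recognised toxicity. None detects a fall that nobody has measured.
- PLD suitability and contraindications (13.1 inclusion 2; 13.2 exclusion 1) defer to local prescribing information, which is not in the documents.

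So the route is open on the text.

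**2. How old can the scan be?**

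Inputs: 6 months × 30.4375 days (SAP 3.1) = 182.6, taken as 183 days; screening Day -28 to Day -1; cytotoxic washout 21 days before first dose; Cycle 0 to Cycle 1 gap 3 to 7 days (SAP 3.1); 28-day cycles; a -7 day window for the Cycle 4 scan (footnote k). Assumption: 15.2 means up to 6 months, since it does not say within.

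- Scan age at first AZD7648 dose, at the limit: 183 + 1 = 184 to 183 + 28 = 211 days.
- Days after that scan open to permitted cytotoxic therapy: 184 - 21 = 163 to 211 - 21 = 190.
- The same for a scan inside the screening period: at most 28 - 21 = 7 days.
- Oldest scan at first PLD dose (Cycle 1 Day 1): 211 + 3 = 214 to 211 + 7 = 218 days.
- Longest gap to the next scheduled LVEF: Cycle 4 Day 1 is 3 × 28 = 84 days after Cycle 1 Day 1, so 211 + 3 + 84 - 7 = 291 to 211 + 7 + 84 = 302 days.

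**3. A mid-range case.** Assume a scan 91 days before screening and screening on Day -14.

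- Age at first dose: 91 + 14 = 105 days. Open to cytotoxics: 105 - 21 = 84 days, room for three 28-day PLD intervals.
- Interval covered by the Cycle 4 change from baseline: 105 + 3 + 84 - 7 = 185 to 105 + 7 + 84 = 196 days. The share before study drug is 105/196 = 54% to 105/185 = 57%.
- If the scan had been done on Day -14: 14 + 3 + 84 - 7 = 94 to 14 + 7 + 84 = 105 days, with a pre-study share of 14/105 = 13% to 14/94 = 15%.

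The open days count any permitted cytotoxic. How many patients received anthracycline in them cannot be derived from the documents.

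**The case against.** The strongest reply is that the waiver is a deliberate clinical rule with safeguards around it. The SoA row cites 15.2. The investigator must judge cardiac status, examine the patient, record an ECG at screening and review LVEF. Core exclusions remove known cardiac disease. Local PLD labelling may itself call for a current LVEF after anthracycline. A site that follows footnote k or Section 8 literally would do a fresh scan anyway.

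Most of this stands, and it makes the gap narrow. It does not close it, because these safeguards rely on known disease, symptoms, ECG or a source outside the documents, and neither footnote k nor Section 8 says how it relates to 15.2.

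A reader might go further and infer that the SAP leaves the LVEF baseline undecided, because its Table 4 has a baseline row running from Day -28. The documents do not support that. SAP 3.1 defines baseline, for safety as well as efficacy, as the last non-missing value before the Cycle 0 Day 1 dose, and treats it as missing only when no earlier value exists. Table 4 is introduced as the windows that follow baseline. The separate 28-day rule for tumour scans applies to tumour scans only. A recorded earlier scan is therefore the LVEF baseline.

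Nor do the documents show that anthracycline-treated patients actually entered on old scans; they give no count.

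**Conclusion.** The protocol point holds. As written, 15.2 allows a Part A patient to qualify for PLD on an LVEF measured before anthracycline exposure, and no criterion in the documents prevents it. The bound is a scan about 211 days old at first AZD7648 dose with about 190 days open to permitted cytotoxics, on the up-to-6-months reading and a 183-day half-year.

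The practical impact is modest. The frequency of waiver use is unknown. Cycle 1 DLT decisions do not depend on LVEF scheduling, since the first on-treatment scan is at Cycle 4. The safety analysis is descriptive (SAP 4.2.1) and LVEF is listed by visit. SAP 1.1 records that development was halted, so the protocol edit matters only while the module enrols.

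On the analysis side the baseline rule is settled. What remains is interpretation: where the baseline is an old scan, part of the tabulated change precedes study drug (54 to 57% in the assumed mid-range case). This is a cheap improvement to patient safety, not a flaw that undermines the module's conclusions.

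**What to change.** **Protocol 15.2:** void the waiver if any anthracycline or other cardiotoxic therapy was given after the earlier scan. **Table 13 footnote k (Parts A and B):** cross-reference 15.2, so that the schedule and the waiver agree. A blanket 28-day limit on earlier scans is not needed.

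Cost: one clause and one cross-reference, with IRB/IEC approval under Appendix A 1. Some pretreated Part A patients would have the screening scan that the SoA already schedules.

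**SAP 3.2.1.12 (optional):** flag in the LVEF change tables any patient whose baseline scan is more than 28 days before Cycle 0 Day 1 or was followed by anthracycline. This needs no new data if scan dates and prior anthracycline dates are in the eCRF, which the documents do not state. If the scan is recorded, the study day that SAP 3.1 puts in the listings already shows its age, so the gain is in the summary tables only.
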